8. ADVERSE EVENTS

8.1 Expected Adverse Events

In a 90-day clinical study, the most commonly reported adverse reactions to Natesto™ were “prostate specific antigen (PSA) increased, headache, rhinorrhea, epistaxis, nasal discomfort, nasopharyngitis, upper respiratory tract infection (URI), sinusitis, bronchitis and nasal scab”² Natesto™ in large doses may lower sperm count and occasionally lead to azoospermia.

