6. PATIENT SELECTION/ELIGIBILITY CRITERIA

6.1 Inclusion (Eligibility) Criteria

Subjects must meet the following criteria:

1. Voluntarily sign and date the study consent form(s) which have been approved by an Institutional Review Board (IRB). Written consent must be obtained prior to the initiation of any study procedures.
2. Male between 18 and 55 years of age, inclusive, with documented onset of hypogonadism prior to age 55.
3. Documented diagnosis of primary hypogonadism (congenital or acquired) or hypogonadotropic hypogonadism (congenital or acquired).
4. Serum total testosterone < 350 ng/dL based on 2 consecutive blood samples obtained 1-4 weeks apart between 6 and 10 AM following an appropriate washout of current androgen replacement therapy; with clinical symptoms of hypogonadism such as diminished energy and sexual function; and/or a decreased sperm count (<20 million sperm/mL semen).
5. Naïve to androgen replacement or has discontinued current treatment and completed a washout of 4 weeks following androgen treatment (excluding Testopel TM). Washout must be completed prior to collection of baseline serum testosterone samples to determine study eligibility.
6. Judged to be in good general health as determined by the principal investigator based upon the results of a medical history, physical examination, vital signs, and laboratory profile and a 12-lead electrocardiogram (ECG) performed at the time of enrolment of within the previous 6 months.

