6.2 Exclusion (Eligibility) Criteria

Subjects meeting any of the following criteria will be excluded from the study:

1. History of significant sensitivity or allergy to androgens, castor oil or product excipients.
2. Clinically significant findings in the pre-study examinations including abnormal breast examination requiring follow-up.

3. Abnormal prostate digital rectal examination (DRE) with palpable nodule(s) or I-PSS score > 19 points.
4. Body mass index (BMI) ≥ 35 kg/m².
5. Azoospermia or severe oligospermia (<1 million sperm/cc) on screening semen analysis: no sperm found in direct nor centrifuged semen sample or previous history of vasectomy.
6. Clinically significant abnormal laboratory value, in the opinion of the investigator, in serum chemistry, hematology, or urinalysis including but not limited to:
 - a. Baseline hemoglobin > 16 g/dL
 - b. Hematocrit < 35% or > 50%
 - c. PSA > 4 ng/mL and age >40
7. History of seizures or convulsions, including febrile, alcohol or drug withdrawal seizures.
8. History of any clinically significant illness, infection, or surgical procedure within 4 weeks prior to study drug administration.
9. History of stroke or myocardial infarction within the past 5 years.
10. History of, or current or suspected, prostate or breast cancer.
11. History of diagnosed, severe, untreated, obstructive sleep apnea.
12. History of abuse of alcohol or any drug substance in the opinion of the investigator within the previous 2 years.
13. History of nasal disorders such as nasal polyps; nasal septal perforation; nasal surgery; nasal trauma resulting in nasal fracture within the previous 6 months or nasal fracture that caused a deviated anterior nasal septum; sinus surgery or sinus disease
14. Donation or loss of 550 mL or more blood volume (including plasmapheresis) or receipt of a transfusion of any blood product within 12 weeks prior to the start of treatment.
15. Inadequate venous access for collection of serial blood samples required for pharmacokinetic profiles.
16. Receipt of any investigational product within 4 weeks or within 5 half-lives prior to the start of treatment.

17. Inability to understand and provide written informed consent for the study.
18. Considered by the investigator or the sponsor-designated physician, for any reason, that the subject is an unsuitable candidate to receive Natesto.
19. History of treatment with clomiphene citrate within the last 12 months.
20. History of varicocele repair.

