7.3 Pre-Treatment Procedures and Evaluations

Upon evaluating the inclusion/exclusion criteria, patients will be recruited to the study. Patients will be instructed to stop any use of androgen replacement for 4 weeks prior to first treatment session and refrain from using any other androgen replacement therapy option during the study. After the washout period and before the first treatment session, patients will answer the IIEF-EF and SF-36 questionnaires for baseline evaluation.

7.4 Follow-Up Procedures and Evaluations:

Follow-up visits will be conducted at week 14+/- 7 days and 26+/- 7 days, these visits shall include:

- Measuring IIEF-EF and SF-36 scores of patients at the clinic
- Taking serum FSH, LH, E, and total Testosterone levels
- Semen analysis
- Reporting and recording adverse events at every follow-up visit.

Additional determinations of total serum testosterone will be performed periodically at every follow up visit, beginning one month after initiation of therapy. Additional semen analysis will be performed at weeks 15+/- 7 days and 27+/- 7 days.

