8.2 Serious Adverse Events

Serious injury or death

Any adverse event and eventual complication must be recorded at any time during the treatments and the follow up visits, and throughout the entire study duration. Patients will be instructed to alert the study investigator by telephone of any side effects occurring in the period after the treatment and until the study end.

For Reporting of adverse events see section 9

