11.7 Non-Protocol Research

No investigative procedures other than those described in this protocol will be undertaken on the enrolled subjects without the agreement of the IRB.

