12. STUDY CALENDAR

| Visit #, Time | Visit 1 (Week 1) Screening | Visit 2 (Week 2) | Visit 3 (Week 6) | Visit 4 (Week 14) | Visit 5 (Week 15) | Visit 6 (Week 26) | Visit 7 (Week 27) |
|--------------------------------------|-------------------------------|---------------------|---------------------|----------------------|----------------------|----------------------|----------------------|
| Medical & Urological History | • | | | | | | |
| Physical Examination & Questionnaire | • | | | • | | • | |
| Informed Consent | • | | | | | | |
| Inclusion & Exclusion Criteria | • | | | | | | |
| Blood Analysis (FSH, LH, T, E) | • | | • (Only T) | • | • (Only T) | • | • (Only T) |
| Semen Analysis | • | • | | • | • | • | • |
| Drug dispensing | | • | | • | | | |

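### PSA increase is a listed common reaction to the study drug, but none of the five blood draws after dispensing includes PSA, so a rise would be found only if clinical care happened to test for it.

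*Combined protocol and SAP*

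**What the plan says.** Section 8.1 quotes ten reactions from a 90-day study of the drug. The list opens with "prostate specific antigen (PSA) increased, headache, rhinorrhea, epistaxis" and continues with nasal, respiratory and sinus complaints.

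PSA appears in one other place, exclusion 6c in section 6.2: "PSA > 4 ng/mL and age >40". Inclusion 6 in section 6.1 asks for good general health judged on "medical history, physical examination, vital signs, and laboratory profile", without naming PSA. The age range is "Male between 18 and 55 years of age, inclusive".

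For the two main follow-up visits, section 7.4 specifies "Taking serum FSH, LH, E, and total Testosterone levels", plus additional testosterone measurements. The only blood row in the calendar is headed "Blood Analysis (FSH, LH, T, E"; that panel falls at Visits 1, 4 and 6, and Visits 3, 5 and 7 have testosterone alone. Drug is dispensed at Visits 2 and 4.

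On capturing events, section 8.2 says: "Any adverse event and eventual complication must be recorded at any time during the treatments and the follow up visits". It also asks patients to telephone with side effects. Section 9 describes ongoing review and specifies database entry for grade 3 to 5 and serious events. It schedules no laboratory safety test.

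**The concern.** Section 7.1 gives evaluating safety as an aim, and section 3.2 includes watching for adverse effects throughout the study. The routes provided are event recording at visits, telephone reports and a physical examination at Visits 4 and 6. These find what a man notices or an examiner sees; none of them yields a PSA value. A site that followed the plan exactly could treat a man for the full course without learning that his PSA had risen, including a man admitted just under the entry limit who then crossed it.

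The reporting consequence is that any PSA rises in the study record would come from whichever men happened to be tested elsewhere. The number tested would be undefined, and a reader could take few or no reported rises as reassurance when PSA had not been measured.

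**Working it through.** The plan states no figure to reproduce. The check is a count of scheduled tests, a classification of the listed reactions, and the timing of two visits.

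**1. Scheduled blood after first dispensing (section 12, Visit 2 in Week 2)**

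| Visit | Week | Blood tests | PSA |
|---|---|---|---|
| 3 | 6 | T | no |
| 4 | 14 | FSH, LH, T, E | no |
| 5 | 15 | T | no |
| 6 | 26 | FSH, LH, T, E | no |
| 7 | 27 | T | no |

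Draws: 5. Draws with PSA: 0. Section 7.4 agrees with the calendar.

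**2. Which listed reactions need a laboratory test (section 8.1)**

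The ten are PSA increase, headache, rhinorrhea, epistaxis, nasal discomfort, nasopharyngitis, upper respiratory infection, sinusitis, bronchitis and nasal scab. Nine are symptoms or clinical diagnoses that a patient can report or an examination can find. 10 − 9 = 1 needs a laboratory test, and it is PSA increase. Section 8.1 separately mentions lowered sperm count. That has scheduled semen analyses at Visits 4 to 7, although it is also a study outcome.

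**3. What is known at baseline**

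Exclusion 6c cannot be applied to a man over 40 without a PSA value. The eligibility checklist in section 5.2 and the source-document rule in section 11.5 imply that the value is on file. It is not a dated item in the calendar, and nothing assures a value for men aged 40 or under.

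**4. Exposure at the visits where PSA could be added**

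Assume dosing starts at dispensing in Week 2.

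- Visit 4: (14 − 2) × 7 = 84 days; with the ±7-day window, 77 to 91 days. Only days 90 and 91 of that window reach 90 days.
- Visit 6: 26 − 2 = 24 weeks, the end of the treatment course in section 4.2.

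**5. Number of added on-treatment assays**

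Two per man. The protocol gives two enrolment figures: 40 (section 4.1) and 80 (sections 6.3 and 10.3).

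- 2 × 40 = 80
- 2 × 80 = 160

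These are ceilings. The documents give no age distribution, so the saving from limiting the test to men over 40 cannot be calculated.

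**The case against.** The strongest case against is that this is a small matter. Section 8.1 gives no rate, size or clinical consequence for PSA increase, so the counts above show an omission and do not measure harm. Section 3.2 promises monitoring and does not promise a frequency for each reaction. Men are at most 55 and are treated for 24 weeks. Section 6.2 excludes known or suspected prostate cancer, palpable nodules, and PSA above 4 ng/mL over age 40. Examinations at Visits 4 and 6, in a urology clinic, could prompt a clinical PSA test. All of this stands and limits the weight of the point. It does not close the gap: an examination measures no PSA, the protocol does not say that it includes the prostate, and a test prompted by chance is still not systematic.

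Three stronger readings are tempting, and the documents do not support them.

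- A reader might infer from section 11.7 that PSA could not be measured at all: "No investigative procedures other than those described in this protocol will be undertaken on the enrolled subjects without the agreement of the IRB". That sentence concerns investigative procedures and does not address clinically indicated testing. Its requirement of IRB agreement applies to any added study test.
- A reader might infer that no baseline PSA exists. Exclusion 6c implies one for men over 40, and the list of reviewed blood tests in section 7.2 is not written as complete.
- A reader might infer that a Visit 4 sample would match the exposure in the 90-day study. Nominally it falls six days short (90 − 84 = 6); Visit 6 is the draw that clearly exceeds it.

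**Conclusion.** The point holds as a gap in safety measurement. The one laboratory-only reaction among the ten listed is measured at none of the five draws after dispensing, so detection depends on testing outside the study plan, and the monitoring in section 9 would have no systematic PSA data to review.

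The primary analysis is unaffected. No event rate or probability of detection can be stated, because the documents supply none. A reader might infer that the study could otherwise have established whether the drug raises PSA. It could not: no control arm is described (the groups A and B in section 10.4 are not defined anywhere), so even complete PSA data would be descriptive.

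The conclusion assumes that the calendar and section 7.4 list all scheduled blood tests. They agree with each other, and nothing elsewhere in the protocol adds one. The change is worth making because it is cheap and uses blood already being drawn.

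**What to change.** For men over 40, the group to which exclusion 6c applies:

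1. In section 12, record the value and date of the eligibility PSA at Visit 1.
2. In sections 7.4 and 12, add PSA to the existing draws at Visit 4 and Visit 6.
3. Have the investigator review each result on arrival. Record a confirmed value above 4 ng/mL (the protocol's own entry limit), or another rise judged clinically significant, as an adverse event under section 8.2 whatever its grade. The grade needs stating because section 9 specifies database entry only for grade 3 to 5 and serious events.
4. In section 10.4, summarise change from baseline, which also shows rises that stay below the limit, and the number of men crossing 4 ng/mL. Use the number tested as denominator and make no causal claim.

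The age limit leaves men aged 40 or under untested. This is a deliberate choice that follows the scope of the protocol's own PSA criterion, and the report should say so.

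Cost: the two on-treatment assays per man counted above, fewer with the age limit; IRB agreement; and clinical follow-up of some abnormal results that have nothing to do with treatment. No new visit or venepuncture is needed.

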8.2 Serious Adverse Events

Serious injury or death

Any adverse event and eventual complication must be recorded at any time during the treatments and the follow up visits, and throughout the entire study duration. Patients will be instructed to alert the study investigator by telephone of any side effects occurring in the period after the treatment and until the study end.

For Reporting of adverse events see section 9

9. DATA AND SAFETY MONITORING PLAN

The study investigators will report to a surgeon monitor [name] in the department of urology (who is not involved in the study) to ensure data quality and subject safety. The investigators will conduct continuous reviews of the data and subject safety, keeping track of the number of subjects, significant toxicities in accordance with the protocol and observed responses, which will be discussed at research committee meetings. All grade 3-5 adverse events (CTCAE v4.0) , will be entered into study database and reviewed at research committee meetings. In addition, all adverse reactions considered “serious” will be entered into research database and reviewed by the Surgeon monitor on an ongoing basis. If a death occurs within 30 days of treatment and is determined to be related to the study, the investigators will notify the Department Chair [name] within 1 business day. If an increase in the frequency of grade 3 or 4 adverse events is noted in the study, a report will be submitted to the Department Chair [name] at the time the increased rate is identified. If at any time the principal investigator stops enrollment or stops the study due to safety issues, the Department Chair ([name]) will be notified within 1 business day and a formal letter will be sent to the Department Chair ([name]) to be received within 10 business days. Additionally to reporting to the Department chair, all serious events will also be reported to the supervising IRB in the same timely manner.

10. STATISTICAL CONSIDERATIONS

10.1 Primary Study Endpoints

The primary endpoint will be change in FSH, LH, Testosterone, and Semen Analysis after 6 months of treatment of Natesto.

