1.3 Study Rationale

Current advantages to Natesto TM include ease of delivery and decreased risk of the medication being transfer upon skin contact to woman or children.¹¹ Recently Natesto 4.5% NTG (125 uL/nostril, 11.0mg testosterone/dose) TID dosing was shown to also increase serum testosterone while maintaining normal, though decreased, serum levels of LH and FSH.¹⁶ This has the

theoretical benefit of maintaining normal semen parameters while on TRT with Natesto- to date, this theoretical benefit has not been evaluated.

While Natesto has been shown to have positive effects on Testosterone while maintaining LH and FSH, the impact on sperm count has not yet been proven. Past research has shown a marked reduction in spermatogenesis in topical testosterone gel treatment.¹⁷ Natesto™ has the potential to maintain normal spermatogenesis levels via maintenance of FSH and LH levels in the normal range. Our hypothesis is that Natesto™ will significantly increase Testosterone while having no significant impact on FSH, LH, and serum parameters in men with Low testosterone. A proposed mechanism for this is that the TID dosing of Natesto will maintain pulsatile release of GnRH, preventing marked decreases in serum FSH and LH.

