2. HYPOTHESIS

2.1 Alternate hypothesis

Natesto™ will not change sperm count by $\pm 10\%$ from baseline.

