2.2 Null Hypothesis

Natesto™ will change sperm count by $\pm 10\%$ from baseline.

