3. OBJECTIVES

3.1 Primary Efficacy Objective

Primary outcomes will be changes in LH, FSH, testosterone, estrogen, and quality of life from baseline, 14 weeks ± 7 days and 26 weeks ± 7 days.

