3.2 Secondary Efficacy Objective

Secondary outcomes will be changes in sperm count from baseline, 14 weeks ± 7 days, and 26 weeks ± 7 days after treatment, as well as monitoring for adverse effects throughout the duration of our study.

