10.2 Endpoint definitions

In the semen analysis, we will include changes in the following parameters: Semen volume (ml), sperm concentration ($\times 10^6$), sperm motility (% progressive), sperm morphology (% normal forms) and sperm viability (% viable); as exploratory endpoints.

Total testosterone will be expressed in ng/dL, and FSH and LH in mIU/mL. Hormone determinations will be done by peripheral venous puncture blood draw.

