10.4 Statistical Analysis and Power calculation

The average and standard deviation of all relevant variables and baseline characteristics, primary and secondary outcomes will be calculated.

Change in sperm count will be analyzed using the ANOVA and MANOVA. A change in $< \pm 10\%$ will be reject the null hypothesis.

LH, FSH, E and Testosterone levels will be analyzed using one-sample t-test with repeated measures throughout the study.

IIEF-EF and SF-36 questionnaires will be analyzed and compared between the groups according to Fisher's exact test in each of the endpoints. The statistical significance will be set at $P < 0.05$.

Demographic characteristics such as age and testosterone level will be compared between groups A and B using student's test. Other demographic characteristics, such as medical background and risk factors will be compared between these groups using Fisher's exact test.

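### The plan contradicts itself on the rank of the sperm result and on the primary endpoint, so no single result is fixed as deciding success

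*Combined protocol and SAP*

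**What the plan says.** Six sections of the combined protocol and SAP bear on the rank of the sperm result or on what is primary.

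- **2.1 and 2.2.** The alternative is that the drug "will not change sperm count by" ±10% from baseline; the null is that it "will change sperm count by" that amount. These are the only formal hypotheses.
- **3.1.** "Primary outcomes will be changes in LH, FSH, testosterone, estrogen, and quality of life from baseline", at weeks 14 and 26. Sperm is not listed.
- **3.2.** "Secondary outcomes will be changes in sperm count from baseline", at the same two visits.
- **10.1.** "The primary endpoint will be change in FSH, LH, Testosterone, and Semen Analysis after 6 months of treatment of Natesto". Estrogen and quality of life are not listed.
- **10.2.** Five semen parameters (volume, concentration, motility, morphology, viability) are included "as exploratory endpoints".
- **10.4.** "Change in sperm count will be analyzed using the ANOVA and MANOVA". A change smaller than ±10% rejects the null. Significance is set at P < 0.05, with no ranking and no testing order.

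Section 1.3 also states a hypothesis in words, this time about hormones: the drug "will significantly increase Testosterone while having no significant impact on FSH, LH, and serum parameters".

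**The concern.** A confirmatory claim needs one result, or one stated combination of results, that decides success before the data are seen. Here each section is clear by itself, but together they cannot be followed.

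Section 1.3 says that maintenance of semen parameters on this drug has not yet been evaluated, so sperm is the trial's central new question. A favourable sperm result could be reported as primary by citing 10.1. An unfavourable one could be reported as secondary by citing 3.2, or as exploratory by citing 10.2. Each report would match one section and contradict others. The same holds for estrogen, quality of life and every week 14 result, which are primary in 3.1 and absent from 10.1.

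**Working it through.** **Step 1. Rank of the sperm result, section by section.**

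| Section | Item named | Status |
|---|---|---|
| 2.1, 2.2, 10.4 | sperm count, ±10% | only formal hypothesis, own decision rule |
| 3.2 | sperm count | secondary |
| 10.1 | semen analysis | primary |
| 10.2 | five semen parameters, including concentration | exploratory |

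That is three ranks plus a formal hypothesis. Applying the 10.2 label to sperm count requires count and concentration to be the same quantity. This is an inference: 1.1 and 6.1 both give sperm count per mL. The conflict between 3.2 and 10.1 does not depend on it.

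**Step 2. Overlap of the two primary lists.** Take 6 months in 10.1 as week 26, and count quality of life and semen analysis once each.

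- 3.1: 5 outcomes × 2 visits = 10 pairs.
- 10.1: 4 outcomes × 1 visit = 4 pairs.
- In both: LH, FSH and testosterone at week 26 = 3 pairs.
- In either: 10 + 4 − 3 = 11 pairs.

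So 3 of 11 pairs are primary in both sections. This measures disagreement in wording, not bias.

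**Step 3. What making sperm the primary would ask of the sample.** The plan gives no SD, power or expected effect, so there is no figure of its own to reproduce. Assume a log ratio of week 26 to baseline with SD 0.2 to 0.5, a true ratio of 1 and complete data. Success means that the 90% CI for the geometric mean ratio lies within 0.90 to 1.10. On the log scale the limits are ln 0.90 = −0.1054 and ln 1.10 = 0.0953.

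Example, N = 80 and SD 0.4:

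- SE = 0.4/√80 = 0.0447.
- CI half-width = 1.664 × 0.0447 = 0.0744.
- The mean log ratio must lie between −0.1054 + 0.0744 = −0.0310 and 0.0953 − 0.0744 = 0.0209, that is between −0.69 and 0.47 SE.
- The normal probability of that interval is about 0.43.

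Simulation with the SD estimated (1,000,000 draws) gives:

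| Assumed SD | 0.2 | 0.3 | 0.4 | 0.5 |
|---|---|---|---|---|
| N = 40 | 85% | 33% | 3% | 0.1% |
| N = 80 | 99% | 81% | 43% | 12% |

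Both sizes are shown because 4.1 gives 40 and 10.3 gives 80.

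**Step 4. Which baseline sample.** The study calendar has semen samples at Visits 1 and 2. Visit 1 is screening. Exclusion 5 in 6.2 removes men below 1 million/cc on the screening sample, and 6.1 allows entry through a count below 20 million/mL. Selecting men on a noisy low value makes later values rise without any drug effect. Assume a population median of 20 to 30 million, a between-man log SD of 0.8 to 1.0, a within-man log SD of 0.3 to 0.5, and, as the extreme case, entry of every man through the low-count route judged at Visit 1. The expected ratio with no drug effect is then 1.03 to 1.16 if baseline is the geometric mean of Visits 1 and 2, and 1.00 if baseline is Visit 2 alone. The upper end exceeds the whole 1.10 limit.

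**The case against.** The strongest reply has four parts.

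- **A hypothesis is not a rank.** A formal null on a secondary outcome is unusual but not contradictory. This stands: a reader might count four ranks, but the text supports three ranks plus a hypothesis.
- **10.2 may concern only the component breakdown.** Semen analysis as a whole could be primary and its parts exploratory, and 10.2 never uses the term sperm count. This is a possible reading, but it does not resolve the conflict. No composite semen measure is defined, concentration is itself one of the exploratory parts, and 3.2 still makes sperm count secondary.
- **The sperm analysis is partly fixed.** Section 10.4 gives sperm count a rule whatever its rank, 3.2 names week 26, and 7.4 calls the week 15 and week 27 samples additional. This stands. Combining two baseline samples or their mean with two late samples or their mean gives 3 × 3 = 9 versions of the change, and a reader might infer that all nine are open. They are not equally open, because 3.2 points to Visit 6. The choice of baseline is what remains unstated.
- **Choosing the rank afterwards is a possibility, not a finding.** This also stands. Nothing in the documents shows that it was done or intended.

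A reader might also infer a specific inflation of type I error, such as 1 − 0.95⁴ = 18.5% for the four items in 10.1. The documents do not support that figure. It needs independent tests and a rule that any one success suffices, and the plan states no success rule. For sperm count, LH and FSH the hoped-for result is also no change.

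**Conclusion.** The contradiction is in the operative text and should be removed before analysis. Three ranks and a formal hypothesis attach to the sperm result, the two primary lists share 3 of 11 outcome-by-visit pairs, and no section says which result decides success. The core finding rests on wording alone: 3.2 against 10.1, and 3.1 against 10.1. Only the exploratory label on sperm count needs the inference that count means concentration. The equivalence probabilities and the regression-to-the-mean range rest on assumed SDs and selection. They bear on the choice of remedy, not on whether the conflict exists. The 40 versus 80 patients and the method for missing data are separate issues.

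**What to change.** Before analysis, put one identical ranked endpoint list in 3.1, 3.2, 10.1 and 10.2, and make Section 2 and 10.4 match it.

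The list that fits Section 2 is:

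- **Primary (one):** change in sperm concentration, stating that sperm count means this, from the Visit 2 sample to Visit 6 (week 26), as a log ratio. State that the Visit 2 sample is taken before the first dose. Success if the 90% CI for the geometric mean ratio lies within 0.90 to 1.10. This replaces the ANOVA/MANOVA rule in 10.4 for this endpoint.
- **Baseline:** leave Visit 1 out, because eligibility is judged on the screening sample.
- **Zero counts:** state in advance how they enter the log ratio, since 8.1 says that azoospermia can occur.
- **Weeks 15 and 27:** supportive only.
- **All other outcomes:** LH, FSH, testosterone, estrogen, quality of life, the other semen parameters and all week 14 results are secondary or exploratory, with CIs and no confirmatory claim.

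If the sponsor prefers a hormone as primary, it must name one hormone at week 26 and rewrite Section 2, 10.1 and 10.4 to match.

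The cost is wording and no new samples, but fewer results can be called primary. With sperm as primary, the chance of success depends heavily on an SD that the documents do not give, as the table in the working shows. The sponsor should make the choice with those figures in view.
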